#### 9.6 Patient Characteristics and Significant Protocol Violations

Demographic and other baseline data will be summarized descriptively for all patients in the ITT set. Comparisons between the two groups will be performed using Pearson’s chi-square tests and Student’s t-tests. Significant protocol violations will be documented.

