### 3.0 STUDY DESIGN

#### 3.1 Overview

Our objectives will be met by performing two studies. The first is a 10-week, randomized, controlled, single-blinded, two-arm, parallel group, pilot trial at a single center and the second is a cross-sectional two-group comparative study.

Study I: A total of 40 persons with HIV may be screened and consented to identify the 32 participants to be enrolled and randomized into the pilot trial. These participants will be  $\geq 18$  years old, have been receiving antiretroviral therapy for at least three months with an HIV viral load  $< 75$  copies/mL, and have an ISI score  $\geq 11$ . These participants will be randomized 1:1 (stratified by age  $<40$  vs.  $\geq 40$  years) to either insomnia treatment with the SHUTi cognitive behavioral therapy program (N=16) or usual care (N=16).

Study II: The 32 participants with insomnia from Study 1 will then be compared to a similar group of 12 HIV-infected patients but with an ISI score  $< 11$ . Six will be  $<40$  years old and the other six will be  $\geq 40$  years old). Approximately 15 persons with HIV may be screened to identify this second group of 12 participants without insomnia.

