### 3.3 Study I Randomization

For those patients eligible for the pilot trial in Study I, they will be randomized at their Entry Visit. Randomization will be stratified by age (<40 years and  $\geq 40$  years). The randomization sequence will be placed in opaque envelopes that will only be opened and witnessed at the Entry Visit.

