#### 9.11 Analysis Plan for Secondary Objectives

Both unadjusted comparisons and adjusted comparisons between UC and SHUTi will be performed for secondary outcomes. Safety assessments will be performed using the safety dataset.

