## 10.7 Inclusion of Women and Minorities

There are no exclusion criteria based on gender, racial category, or ethnicity. Based on our previous cumulative experience and the general HIV-infected population cared for at the study sites at the Indiana University Health Medical Center (Eskenazi Hospital, Methodist Hospital, VA Roudebush Hospital, and Indiana University Health Hospital), it is anticipated that approximately 25% of the study participants will be women.

It is also anticipated that approximately 50% and 10% of the study participants will be black and Hispanic, respectively. American Indians, Alaskan Natives, Asians, Native Hawaiians or Other Pacific Islanders are not expected to be represented in the proposed study population due to extremely low representation of these groups within the Indiana University Health Hospitals HIV outpatient clinics and in Indianapolis in general.

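### Section 9.6 tests baseline differences between randomised arms, where the null is true by design, and no adjustment covariates are fixed for the secondary comparisons (minor)

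*Combined protocol and SAP*

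**What the plan says.** Section 9.6 starts with a descriptive table: "Demographic and other baseline data will be summarized descriptively for all patients in the ITT set". It then adds tests: "Comparisons between the two groups will be performed using" Pearson's chi-square for categorical variables and Student's t for continuous ones. Section 9.5 defines the ITT set as eligible, randomised patients, so the two groups are SHUTi and Usual Care and not the insomnia and non-insomnia groups of Study II. Section 9.6 gives no significance level, list of variables or multiplicity rule, and does not say what the p-values are for.

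Section 3.1 sets the allocation as "either insomnia treatment with the SHUTi cognitive behavioral therapy program (N=16) or usual care (N=16"). Section 3.3 adds: "Randomization will be stratified by age", cut at 40 years.

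Section 9.10 specifies the primary model as an ANCOVA of Week 10 ISI on treatment group and baseline ISI, with no term for age stratum. For secondary outcomes, Section 9.11 says only this: "Both unadjusted comparisons and adjusted comparisons between UC and SHUTi will be performed for secondary outcomes". It does not name the adjustment variables. Section 9.1 allows the analysis plan to change without a protocol amendment unless a significant feature of the study changes.

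**The concern.** A significance test asks whether chance could explain a difference. Between properly randomised arms, chance is the only explanation for a baseline difference, so the answer is known before the data arrive. The resulting p-values can mislead in two ways. A small one draws attention to a variable whether or not it is prognostic. A large one invites the statement that the arms were balanced, which a trial of 32 cannot support.

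The practical stake is adjustment. The secondary comparisons are to be adjusted, but for what is left open, and the 9.6 table would be at hand when the choice is made. Covariates picked because their baseline p-values were small make the adjusted estimates depend on the data. Section 9.2 says that the pilot is meant to show clinically relevant effect sizes, so estimates that can move with an unplanned covariate choice are a weakness, even though formal significance is not the aim.

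**Working it through.** **The plan's own figures.** The plan states no error rate for the baseline tests. The nearest figure that can be reproduced is the expected number of completers in Section 9.2: 16 × (1 − 0.25) = 12 per arm, which agrees. Baseline data precede dropout, so 16 per arm is the relevant size below.

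**Inputs.**
- 16 v 16 (Section 3.1).
- 0.05 two-sided per test. This is an assumption: the plan states that level only for the primary analysis (9.10).
- Number of variables, k. Section 9.6 gives no list. Sections 6.1 and 6.2 name about 35 baseline variables: 6 demographic or HIV-history, 5 physical, 9 laboratory, 11 questionnaires and 4 frailty, function or cognition measures (6 + 5 + 9 + 11 + 4 = 35). How many would be tested is unknown, so a range is shown.

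**Chance of at least one flag, every null being true.** For independent tests this is 1 − 0.95^k. The correlated columns come from a simulation of t-tests at 16 v 16 with a common correlation between variables (4,000 runs).

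| k | Independent | Correlation 0.3 | Correlation 0.5 |
|---|---|---|---|
| 10 | 40% | 35% | 29% |
| 14 | 51% | 45% | 34% |
| 20 | 64% | 54% | 43% |
| 30 | 79% | 68% | 53% |
| 35 | 83% | not run | not run |

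The expected number of flags is 0.05 × k, which is 1.75 at k = 35 whatever the correlation.

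**What a t-test can flag at 16 v 16.** With 30 degrees of freedom the two-sided 5% critical value is 2.042. The standard error of a difference, in SD units, is √(2/16) = 0.354. The smallest observed difference that reaches p<0.05 is 2.042 × 0.354 = 0.72 SD. An observed difference of 0.5 SD gives t = 0.5/0.354 = 1.41 and p = 0.17, so it would always be reported as not significant.

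**Link to adjustment.** Set side by side, Section 3.3 uses age stratum to randomise, Section 9.10 adjusts for baseline ISI only, and Section 9.11 adjusts for unnamed variables. No sentence fixes the secondary covariates in advance or rules out choosing them from the 9.6 table.

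**The case against.** The strongest reply is that nothing depends on these tests. The primary model is already fixed, 9.6 attaches no decision to the p-values, and 9.2 says that significant differences are neither expected nor needed. The adjusted comparisons in 9.11 can be read as following the primary model, that is, adjusting for the baseline value. All of this stands and keeps the point minor. A reader might infer that the plan selects covariates by baseline p-value. It does not say so; it only leaves the way open.

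A second reply is that chance is the only explanation only if allocation was carried out properly. Envelopes are opened on site, and gross imbalance could hint at a breach. That is fair in principle, but 9.6 states no such purpose, and a test that needs 0.72 SD to react is a weak check.

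Third, a reader might infer that a flag is likely. That needs about 14 or more roughly independent variables at 0.05. The level and the list are unstated, and several measures plainly overlap (ISI with PSQI, CD4 count with percentage, creatinine with estimated GFR). With 10 independent variables, or 20 correlated at 0.5, the chance is below one half.

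Fourth, it is tempting to attack the chi-square approximation. Section 10.7 says "it is anticipated that approximately 25% of the study participants will be women" and expects "approximately 50% and 10% of the study participants will be black and Hispanic", so expected counts per arm are 16 × 0.25 = 4.0 women and 16 × 0.10 = 1.6 Hispanic participants. By full enumeration, however, the true size of the nominal 5% test at 16 v 16 is 5.7% for a 25% characteristic and 2.8% for a 10% one: close to nominal in one case and conservative in the other. Fisher's exact test is further from 5%, at 1.9% and 0.7%. At the Study II sizes of 32 v 12 it is also further off (3.2% against 4.7% for chi-square, and 1.4% against 3.3%). The figures give no reason to object to chi-square or to switch to Fisher's test.

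**Conclusion.** The point holds as a minor one. Section 9.6 plans tests of a null that randomisation makes true, and their results can show neither that the arms are balanced nor that adjustment is needed. The chance of at least one flag is 40% to 83% for 10 to 35 independent variables. This rests on an assumed 0.05 per test and an assumed count of variables, and falls with correlation. The 0.72 SD threshold rests only on 16 per arm and the 5% level.

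A reader might also want to quote the power of these tests against a true 0.5 SD difference. That would be the wrong quantity, because randomisation rules out a population difference between arms. What matters is the imbalance observed in the sample, and the threshold describes that.

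The one consequence worth acting on is that the secondary covariates are open and the age stratum is missing from the primary model. The primary analysis does not depend on the baseline tests.

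**What to change.** - **Section 9.6:** delete the sentence on chi-square and t-tests. Report means, SDs and counts by arm, without p-values.
- **Sections 9.10 and 9.11:** state that each model adjusts for the Entry value of the outcome and for age stratum (<40 v ≥40 years), and that these covariates are fixed in advance and not chosen from the baseline table. For the primary outcome, this adds only the stratum to the existing ANCOVA.

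Deleting the 9.6 sentence alone would not be enough, because it leaves the covariates in 9.11 undefined.

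The cost is a few sentences, slightly less analysis work, and one degree of freedom for the stratum. With 12 completers per arm, residual degrees of freedom in a complete-case ANCOVA go from 24 − 3 = 21 to 24 − 4 = 20. With all 32 they go from 29 to 28.

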#### 9.7 Disposition

The number of enrolled subjects will be summarized in a flow chart with frequency of completion and discontinuation. The subjects discontinued from SHUTi and their corresponding information will be listed. Significant protocol violations will be tabulated and/or listed.

#### 9.8 Compliance

Compliance status will be tabulated for the SHUTi arm.

#### 9.10 Analysis Plan for the Primary Objective

To test our primary hypothesis, an analysis of covariance (ANCOVA) will be performed to test for treatment group differences in Week 10 ISI adjusted for baseline ISI using the intent-to-treat set. Statistical significance will be considered if two-sided p-value  $<0.05$ . This analysis will be also repeated using the per-protocol set.

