### DESIGN

Our objectives will be met by performing two studies. The first is a 10-week, randomized, controlled, single-blinded, two-arm, parallel group, pilot trial at a single center and the second is a cross-sectional two-group comparative study.

Study I: A total of 40 persons with HIV may be screened and consented to identify the 32 participants to be enrolled and randomized into the pilot trial. We expect a screen failure rate of 20%. These participants will be  $\geq 18$  years old, have been receiving antiretroviral therapy with an HIV viral load  $< 75$  copies/mL within three months of the Entry Visit, and have an ISI score  $\geq 11$  within three months of the Entry Visit. These participants will be randomized 1:1 (stratified by age  $<40$  vs.  $\geq 40$  years) to either insomnia treatment with the SHUTi cognitive behavioral therapy program (N=16) or usual care (N=16).

Study II: The 32 participants with insomnia from Study I will then be compared to a similar group of 12 HIV-infected patients but with an ISI score  $< 11$  within three months of the Entry Visit. Six will be  $<40$  years old and the other six will be  $\geq 40$  years old). Approximately 15 persons with HIV may be screened and consented to identify this second group of 12 participants without insomnia. We expect a screen failure rate of 20%.

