### 1.3 Study II Primary Objectives

1.3.1 To compare FRAIL scale, Fried Index, and SPPB scores between those with ISI scores  $\geq 11$  and those with ISI  $< 11$ .

1.3.2 To compare CSRQ-25 and Digit Symbol Substitution Test (DSST) scores between those with ISI scores  $\geq 11$  and those with ISI  $< 11$ .

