## 2.3 Study Rationale

Our long-term goal is to use SHUTi as an intervention to treat insomnia in patients with HIV infection in order to improve long-term outcomes (including reducing the risk of cardiovascular disease, frailty, cognitive

functioning, and depression) and quality of life. Our group has extensive experience in cardiovascular disease prevention research (e.g. our currently NIH-funded R01 trial of internet-based CBT depression therapy in HIV to reduce inflammation and improve endothelial function), but we also want to develop research expertise in HIV-related frailty and cognitive impairment, as these are increasingly important outcomes (and areas of interest to the NIH) in the aging HIV population.

There are several R01-level NIH funding mechanisms focused on cardiovascular disease, frailty, cognitive impairment, and depression in HIV (PA-16-427, PAR-17-321). We believe that treating insomnia in HIV is a unique method by which to improve all of these endpoints. But to be competitive for these funding opportunities, we will first need to develop preliminary data showing that SHUTi can be effective both in our hands and in our target population. Of note, we already have preliminary cross-sectional data demonstrating an inverse relationship between more severe insomnia symptoms using the PSQI scale and lower endothelial function (as measured by flow-mediated dilation of the brachial artery in [name] CTSI Vascular Imaging Core) in HIV-infected patients on virologically-suppressive antiretroviral therapy (ART). *However, we need to develop additional preliminary data in a similar group of HIV-infected patients that relate insomnia measures to frailty and cognitive impairment, as these are new areas of research for our group.* If we can demonstrate that insomnia is negatively related to frailty and cognitive impairment in HIV and that SHUTi improves sleep outcomes in this population, then we can more readily justify randomized trials of SHUTi to improve these measures in HIV and thus be more competitive for extramural funding.

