## 9.0 STATISTICAL CONSIDERATIONS AND DATA MANAGEMENT

### 9.1 General Considerations

Data management and statistical analyses will be the responsibility of the study team. The randomization sequence, though, will be generated by a member of the Department of Biostatistics. Parameter estimates and relevant summary statistics will be reported for both efficacy and side effects. Continuous variables will be summarized by means, medians, minima, maxima, and standard deviations. Categorical variables will be summarized by frequencies and percentages. Additional exploratory analyses will be performed when appropriate. Normality of variables will be checked and, if violated, nonparametric methods will be adopted. Changes from the analysis plan will not require an amendment to the protocol unless it changes a significant feature of the study.

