### 9.2 Sample Size Justification

As a pilot trial, no formal sample size estimation was performed as we do not expect to find significant differences in the comparisons to be performed for either Study I or Study II. The sample sizes of 32 participants (40 screened and consented to identify the 32) with insomnia for the Study I trial and the additional 12 (15 screened and consented to identify the 12) participants without insomnia for the comparison studies for Study II should be sufficient as per Julious (34). We expect a dropout rate of 25% for the RCT based on our ongoing study of depression CBT; thus, approximately 12 in each group will likely complete the proposed trial. It is unlikely that there will be sufficient power with just 12 per study arm for statistical hypothesis testing. However, we do not believe it necessary to find statistically significant differences between study arms at this stage as long as we can demonstrate that the SHUTi intervention can be implemented successfully by our group

and that the effect sizes related to differential outcomes in the two study arms are clinically relevant. Of note, the prevalence rate of ISI scores  $\geq 15$  in patients from the Eskenazi HIV clinics who would be eligible for the currently proposed pilot trial is 25%. Given that there are over 800 patients on stable HIV therapy in these clinics and our group’s proven ability to recruit in these clinics, we should have no difficulties enrolling 32 participants with insomnia into the Aim #1 trial.

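### The primary ANCOVA omits the age stratum used to randomise Study I, and Study II has no planned age adjustment although only its 12 controls have an age quota

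*Combined protocol and SAP*

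**What the plan says.** Section 3.3 states: "Randomization will be stratified by age", with the cut at 40 years; the Schema and 3.1 agree. Section 9.1 adds "The randomization sequence, though, will be generated by a member of the Department of Biostatistics". No block size or other within-stratum balancing device is given in either place.

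The primary analysis (9.10) is an ANCOVA "to test for treatment group differences in Week 10 ISI adjusted for baseline ISI using the intent-to-treat set". Baseline ISI is the only covariate named. Section 9.11 says "Both unadjusted comparisons and adjusted comparisons between UC and SHUTi will be performed for secondary outcomes" but lists no covariates, and 9.14 plans multiple imputation without naming the variables in the imputation model.

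For Study II, the Schema says "The 32 participants with insomnia from Study I will then be compared to a similar group of 12 HIV-infected patients". Six of those 12 are to be under 40 and six 40 or over. No age quota applies to the 32. The frailty and cognition comparisons are primary objectives in 1.3 (for cognition, "To compare CSRQ-25 and Digit Symbol Substitution Test (DSST) scores between those with ISI scores" of 11 or more and below 11), yet no part of section 9 sets out how Study II will be analysed.

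**The concern.** A factor important enough to stratify on is normally carried into the model. If age predicts Week 10 ISI beyond baseline ISI, leaving it out keeps its variance in the residual. If allocation is also balanced within strata, the design has already removed the age contribution from the treatment contrast. The model-based standard error is then too large and the test conservative. Section 9.2 does not rely on significance; it asks whether "the effect sizes related to differential outcomes in the two study arms are clinically relevant". Interval width is therefore the relevant quantity.

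Study II is not randomised, so the issue there is bias. Stratified randomisation equalises age between the SHUTi and Usual Care arms; it does not set the age mix of the 32 taken together. A quota on the 12 controls alone can therefore create an age difference between the insomnia and no-insomnia groups. The outcomes are ones the protocol itself ties to ageing: section 2.3 describes "frailty and cognitive impairment, as these are increasingly important outcomes (and areas of interest to the NIH) in the aging HIV population". Section 2.3 also says these results should help justify later randomised trials, so a distorted estimate would carry forward.

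**Working it through.** **Inputs from the documents.** 16 per arm, 1:1, stratified by age (Schema, 3.1, 3.3); 25% dropout and about 12 completers per arm (9.2); two-sided 0.05 (9.10); 32 versus 12 in Study II with a 6/6 control quota (Schema, 3.1).

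**The plan's own counts.** 16 × (1 − 0.25) = 12 per arm; 32/0.8 = 40; 12/0.8 = 15; 40 + 15 = 55. All reproduce. The plan states no power or detectable effect.

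**Assumed, because the documents give no figure.** An age effect of 0.5, 0.8 or 1.0 SD. For Study I: half aged 40 or over, baseline to Week 10 correlation 0.5, blocks of 4. For Study II: a range of age mixes among the 32.

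**Study I.** What matters is the age effect left after conditioning on baseline: (Week 10 shift) − 0.5 × (baseline shift). For a Week 10 shift of g, this is 0.5g if both visits shift equally, 0.75g if the baseline shift is half as large, and g if only Week 10 shifts. Results from 20,000 simulated trials per setting (32 randomised, 8 lost at random, complete-case ANCOVA; percentages from unrounded SEs):

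| Age acts on | Age effect (SD) | SE without / with age | Increase | Type I error without age | Power at 0.8 SD, without / with age |
|---|---|---|---|---|---|
| Both visits equally | 0.5 | 0.363 / 0.362 | 0.3% | 4.8% | 55.0 / 54.9% |
| | 0.8 | 0.368 / 0.363 | 1.4% | 4.7% | 54.0 / 54.8% |
| | 1.0 | 0.371 / 0.362 | 2.4% | 4.3% | 52.7 / 54.2% |
| Half the shift at baseline | 0.5 | 0.368 / 0.362 | 1.7% | 4.9% | 53.8 / 55.1% |
| | 0.8 | 0.381 / 0.362 | 5.1% | 4.2% | 50.8 / 54.3% |
| | 1.0 | 0.392 / 0.362 | 8.2% | 4.0% | 48.2 / 54.7% |
| Week 10 only | 0.5 | 0.376 / 0.363 | 3.7% | 4.3% | 52.3 / 54.7% |
| | 0.8 | 0.399 / 0.362 | 10.2% | 3.7% | 47.8 / 55.2% |
| | 1.0 | 0.419 / 0.361 | 15.8% | 3.3% | 43.6 / 55.5% |

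Hand check of the last row: residual variance is 1 − 0.5² = 0.75, and an omitted 1 SD step at a 50:50 split adds 0.25, so the ratio is √(1 + 0.25/0.75) = 1.155. This agrees with the simulation.

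Absolute bias under the null was at most 0.01 SD throughout. Without blocking, the planned model kept its level (4.8 to 5.3%). With no age effect, adding the stratum raised the SE by 0.6% (blocked) or 2.6% (unblocked).

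A separate simulation (40,000 trials per setting, exact balance within strata, age acting on Week 10 only, residual SD 1, 12 per arm, half aged 40 or over) gave mean 95% interval widths without and with age of 1.77 and 1.72 at 0.5 SD, and 1.94 and 1.72 at 1.0 SD. These are 3% and 13% wider. Type I error without age was 4.4% and 2.9%.

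**Study II.** Unadjusted bias = (share of the 32 aged 40 or over − 0.5) × age effect. For example, 26/32 = 0.8125, so 0.3125 × 0.5 = 0.16 and 0.3125 × 1.0 = 0.31. For scale, √(1/32 + 1/12) = 0.34 SD. With no true difference and 8,000 simulations per setting:

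| Aged 40 or over among the 32 | Bias (SD), age effect 0.5 to 1.0 | False-positive rate, unadjusted |
|---|---|---|
| 16 (50%) | 0 | 2.8 to 4.0% |
| 19 (59%) | 0.05 to 0.09 | 3.5 to 4.4% |
| 22 (69%) | 0.09 to 0.19 | 4.9 to 5.9% |
| 26 (81%) | 0.16 to 0.31 | 6.7 to 10.9% |
| 29 (91%) | 0.20 to 0.41 | 8.2 to 18.4% |

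With the age stratum in the model the bias was about 0 and the rate 4.7 to 5.3%. The separate simulation gave 0.19 to 0.375 SD and 7.7 to 15.6% at 87.5%. With only 25% aged 40 or over, the bias reversed sign: −0.125 to −0.25 SD.

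**The case against.** The strongest reply on Study I is that this is a small matter. Nothing in the documents says age affects ISI. Age group is practically fixed over 10 weeks and the instrument is the same, so equal shifts at both visits are the natural case; there the loss is at most 2.4% in SE, and the cost of adding an irrelevant stratum (0.6 to 2.6%) is of the same order. The conservatism also needs within-stratum balance, which is not stated. The trial is a pilot that disclaims power, and the simulations used complete cases where the plan uses multiple imputation. All of this stands. It makes the Study I part minor, but does not justify leaving the stratification factor out of the model.

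On Study II, the larger gap is that no analysis is described at all; age adjustment is one detail of it. That is correct. The sizes depend on an age mix and an age effect that the documents do not supply, and up to a 69% share the bias is at most 0.19 SD. The removal of bias is partly built in, because the simulated age effect is the same two-level step that the model contains; age differences within the 40-or-over group were not examined. FRAIL and Fried are 0 to 5 counts, so SD-scale figures are only a guide. These points limit the size claimed. The one-sided quota remains, and a pilot's indifference to significance does not excuse a biased estimate.

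**Conclusion.** The point holds. In Study I, leaving out the age stratum causes no bias with complete data or dropout unrelated to age. The loss of precision runs from negligible to moderate depending on how age acts, and any error in the test is conservative. One qualification: with 25% dropout expected, age-related dropout could bias the result if age is also missing from the imputation model.

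In Study II, confounding by age is a risk, not a certainty. It vanishes if half of the 32 are 40 or over, or if age is unrelated to the outcome. It matters mainly if about 80% or more are 40 or over, and it exceeds one standard error (0.34 to 0.38 SD) only at the extreme of the range examined. All sizes rest on the assumptions listed in the working. The change is worth making because it costs almost nothing.

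**What to change.** - **9.10:** fit Week 10 ISI on arm, baseline ISI and age stratum (under 40, 40 or over).
- **9.14:** include the age stratum in the imputation model.
- **9.11:** define the adjusted comparison as adjusting for the baseline value of the outcome and age stratum.
- **Study II, when its analysis is written:** estimate the insomnia versus no-insomnia difference in FRAIL, Fried, SPPB, CSRQ-25 and DSST with age as a covariate, stating whether as stratum or in years, and report the adjusted difference with its 95% confidence interval. If the non-parametric fallback of 9.1 is used, stratify it by age, for example with a van Elteren test. Report the counts under 40 and 40 or over in both groups. Age-adjusted correlations for 1.4.1 are optional.

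The cost is SAP wording and one degree of freedom per model. Birthdate is already recorded (6.2.2), and 9.1 allows analysis changes without a protocol amendment unless a significant feature is altered. If age is not prognostic, the Study I SE rises by 0.6 to 2.6%. In Study II the SE rises from 0.34–0.36 to about 0.38 SD at a 91% share and falls at a 50% share.
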